5.7.3.2 Main Secondary Analysis

The same strategies as those for the primary estimand will be used for the main secondary analysis in the FAS, with castration maintenance criteria being replaced with 0.694 nmol/L (20 ng/dL) whenever applicable.

For binary secondary endpoints, including castration maintenance (<50 ng/dL) rate at specific timepoints, castration maintenance (<20 ng/dL) rate during the study, castration maintenance (<20 ng/dL) rate at each timepoint, castration maintenance rate along with the associated 95% exact CI will be provided. For percent change in PSA from baseline at Day 169 and Day 337, descriptive statistics will be provided.

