5.7.2 Analysis of Primary Efficacy Endpoint

5.7.2.1 Primary Efficacy Endpoint, Treatment Effect and Estimand Definition

To assess the primary objective, the primary estimand will be defined by the following attributes:

- Population: participants with locally advanced and/or metastatic prostate cancer previously treated and castrated with a GnRH analogue as defined by the listed Inclusion/Exclusion criteria in sections 5.1 and 5.2 of the protocol, respectively.
- Variable/Endpoint: castration maintenance rate during the study defined as percentage of participants castrated (testosterone < 1.735 nmol/L (50 ng/dL)) at Day 29, Day 85, Day 141, Day 169, Day 253, Day 309 and Day 337, with two complete study intervention administrations.
- Key Intercurrent event (ICE):
 - (a) ICE 1 - Subjects discontinued from study prior to Day 337 without evidence of inadequate testosterone suppression (testosterone measurement \geq 50 ng/dL)
The testosterone values of these participants will not be considered for the main analysis (principal stratum strategy).
 - (b) ICE 2 - Subjects with at least one planned testosterone measurement missing on or prior to Day 337 without evidence of inadequate testosterone suppression (testosterone measurement \geq 50 ng/dL)
The testosterone values of these participants will not be considered for the main analysis (principal stratum strategy).

Associated Procedure / Instruction Reference	319480-SOP
Form Reference	080091-FOR v7.0

(c) ICE 3 - Subjects discontinued treatment prior to receiving the second study intervention administration without evidence of inadequate testosterone suppression (testosterone measurement ≥ 50 ng/dL)
The testosterone values of these participants will not be considered for the main analysis (principal stratum strategy).

(d) ICE 4 - Subjects received a prohibited medication during the study
Prohibited medication with impacts on the testosterone value will be identified through blinded data review. Subjects receiving identified prohibited medication (for example, finasteride, dustasteride, or abiraterone) will be included in the primary analysis as non-responder. In contrast, all testosterone measurements from subjects receiving prohibited medications other than identified ones during the study will be included in the primary analysis (composite strategy).

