5.7.3 Analysis of Key Secondary Efficacy Endpoints

5.7.3.1 Secondary Efficacy Endpoints

The secondary efficacy endpoints are listed below:

- Percentage of participants castrated at each timepoint on Day 29, Day 85, Day 141, Day 169, Day 253, Day 309 and Day 337 (castration defined as testosterone <1.735 nmol/L (50 ng/dL))
- Percentage of participants with a serum testosterone level <0.694 nmol/L (20 ng/dL) during the study
- Percentage of participants with a serum testosterone level <0.69 nmol/L (20 ng/dL) at each timepoint on Day 29, Day 85, Day 141, Day 169, Day 253, Day 309 and Day 337
- Percentage of participants castrated on Day 3 and Day 7 after each injection administered on Day 1 and Day 169 (castration defined as testosterone <1.735 nmol/L (50 ng/dL))
- Percent change in PSA from baseline (prior to injection) at Day 169 and Day 337 (Percent change in PSA defined as the absolute value of difference between the PSA values at Day 169 and Day 337 and the baseline value divided by the baseline value).

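### SAP 5.7.3.2 carries the prohibited-medication rule (ICE 4) to the by-visit castration rates without an intake date, so on its plain reading a late user counts as not castrated at earlier visits where he was measured castrate

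*SAP*

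**What the plan says.** SAP 5.7.2.1 defines the event as "ICE 4 - Subjects received a prohibited medication during the study". It then separates the drugs: "Prohibited medication with impacts on the testosterone value will be identified through blinded data review". For the drugs so identified, "Subjects receiving identified prohibited medication (for example, finasteride, dustasteride, or abiraterone) will be included in the primary analysis as non-responder"; for other prohibited drugs, all testosterone values are used. The SAP labels this a composite strategy. Neither the trigger nor the consequence mentions an intake date or a visit.

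SAP 5.7.3.2 states that "The same strategies as those for the primary estimand will be used for the main secondary analysis in the FAS". The one adaptation it goes on to name concerns the threshold: "with castration maintenance criteria being replaced with 0.694 nmol/L (20 ng/dL) whenever applicable". No other adaptation is given.

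The secondary endpoints in SAP 5.7.3.1 include "Percentage of participants castrated at each timepoint on Day 29, Day 85, Day 141, Day 169, Day 253, Day 309 and Day 337" at the 50 ng/dL threshold, the same seven visits at the 20 ng/dL threshold, and "Percentage of participants castrated on Day 3 and Day 7 after each injection administered on Day 1 and Day 169".

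Nothing elsewhere limits ICE 4 to visits after intake. Sensitivity analyses S1 to S3 (SAP 5.7.2.3) keep it as in the primary estimand. The visit windows (6.1), the unscheduled-visit rules (6.2), the derived data (7) and the changes from protocol (8) do not mention it.

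**The concern.** ICE 4 is a rule about a man, and a by-visit rate is a statement about a date. For the primary endpoint the two agree: each man has one outcome over all visits, and a disqualifying drug at any time can fairly make that outcome a failure. For the castration rate at Day 29 they do not agree. A drug first taken on Day 300 cannot have affected a Day 29 sample, yet the rule as carried over makes the man a Day 29 failure.

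The by-visit rates are there to show when castration is lost, and the Day 3 and Day 7 rates address the acute-on-chronic objective. Spreading a late intake back over earlier visits adds failures that no sample recorded, and it adds them at the visits where the timing is most informative. If the point is left open, two programmers could also produce different tables from the same data.

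**Working it through.** **1. The plan's own figure, to fix the denominator.** SAP 2.3 gives 130 evaluable men, 97% assumed against 90%, one-sided alpha 0.025, exact binomial, about 90% power, and 145 enrolled with 10% drop-out.
- The smallest success count r with P(X ≥ r | n = 130, p = 0.90) ≤ 0.025 is 124, which gives alpha 0.0207.
- Power is P(X ≥ 124 | n = 130, p = 0.97) = 0.903.
- The Clopper-Pearson lower bound is 90.2% at 124/130 and 89.2% at 123/130.
- Enrolment is 130/0.90 = 144.4, rounded up to 145.

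The design figures reproduce, and 130 is used below as the assumed size of the full analysis set (FAS).

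**2. Which visits are affected.** The schedule has 11 post-dose testosterone visits: Days 3, 7, 29, 85, 141, 169, 171, 175, 253, 309 and 337.
- First intake on Day 300: Days 3, 7, 29, 85, 141, 169, 171, 175 and 253 come earlier, so nine visits. Five belong to the Day 29 to Day 337 series and four to the Day 3/Day 7 endpoint.
- First intake after the Day 309 sample and no later than Day 337: Day 309 is added, so ten visits. This is the maximum.
- The 20 ng/dL rates are not defined at the Day 3 and Day 7 visits, so the counts there are five and six.

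Apart from men with a value of 50 ng/dL or more, the FAS requires testosterone at all seven visits from Day 29 to Day 337. A late user without such a value therefore has real measurements at those earlier visits, and the rule overrides them.

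**3. Size per man.** Each man measured castrate at a pre-intake visit but scored as a failure lowers that visit's rate by 1/130 = 0.77 points. Two give 2/130 = 1.54, three give 3/130 = 2.31 and five give 5/130 = 3.85.

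**4. Illustration at Day 29 (assumed counts, exact 95% CI).** Suppose 126 of 130 men are measured castrate and the late users are among those 126.

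| Late users | Scored castrate | Rate | 95% CI |
|---|---|---|---|
| 0, or rule applied from intake | 126/130 | 96.9% | 92.3 to 99.2 |
| 1 | 125/130 | 96.2% | 91.3 to 98.7 |
| 2 | 124/130 | 95.4% | 90.2 to 98.3 |
| 3 | 123/130 | 94.6% | 89.2 to 97.8 |
| 5 | 121/130 | 93.1% | 87.3 to 96.8 |

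With three late users, 3 of the 7 reported Day 29 failures (130 − 123 = 7) would have no elevated sample behind them. Starting from 129/130 (99.2%, 95.8 to 100.0), three late users give 126/130 (96.9%, 92.3 to 99.2). The documents give no expected number of such men; one to five is an assumed range.

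**The case against.** The strongest reply is that the SAP never says in words that earlier visits are to be scored as failures. The non-responder sentence refers to the primary analysis, and what 5.7.3.2 carries over is a strategy. A composite strategy at Day 29 could mean that the event counts only if it has happened by Day 29. That reading is possible, and a careful programmer might choose it. It does not remove the point: the only rule written down has no time element, and the only adaptation named is the threshold, so following the text gives backward scoring.

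It is also fair that the binary endpoints spelled out in 5.7.3.2 do not name Day 3 and Day 7. Their inclusion follows from their place in the 5.7.3.1 list and from the general wording about specific timepoints, so it is less explicit than for Days 29 to 337.

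Several points limit the weight. SAP 5.7.1.1 plans no formal testing, all raw and derived efficacy data are listed (5.7.1), the error can only lower a reported castration rate, and recent finasteride or dutasteride use is an exclusion (Protocol 5.2). All of this stands and bears on size.

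A reader might go further and infer that PSA values altered by a prohibited drug enter the PSA summary as an effect of triptorelin. The documents do not support that. They do not say that the identified drugs change PSA; the drugs are identified by their effect on testosterone. For PSA the plan says only that "For percent change in PSA from baseline at Day 169 and Day 337, descriptive statistics will be provided". The treatment regimen already includes permitted concomitant medication, among it enzalutamide, apalutamide and darolutamide (SAP 5.7.2.1, Protocol 6.8), so the summary was not built to isolate triptorelin. Summarising observed PSA is a legitimate choice, and dropping post-intake values would remove data selectively.

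**Conclusion.** The point holds for the by-visit castration rates. On the plain reading of SAP 5.7.2.1 and 5.7.3.2 together, a man who first takes an identified prohibited drug late is counted as not castrated at up to ten earlier post-dose visits where he was measured castrate. The cost is 0.77 percentage points per man per visit, which rests on an FAS of 130 and on an unknown number of such men; with none, nothing changes. The distortion is conservative and confined to secondary, descriptive tables.

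A reader might infer that the main result or the sample size is at risk. Neither is: the participant-level rule is coherent for the primary endpoint, and the design figures reproduce. This is a modest gap that should be closed because it blurs the timing these rates are meant to show and leaves the programming open.

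**What to change.** Add to SAP 5.7.3.2 that, for all by-timepoint endpoints (50 and 20 ng/dL at Days 29 to 337, and Day 3 and Day 7 after each injection), ICE 4 non-response applies only at visits on or after the first intake of an identified drug during the study, and that earlier visits are analysed as observed. Keep the participant-level rule for the two during-study endpoints.

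Add a rule for partial intake dates. Appendix 2 imputes medication dates only for prior/concomitant classification and duration, not for placing an intake relative to a visit. Its earliest-possible start date could be reused, which errs towards failure, but the SAP has to say so.

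No new data are needed, since Protocol 6.8 already has medication start and end dates recorded in the eCRF. The cost is one date comparison per visit and by-visit rates that are slightly less conservative. The primary analysis and the sample size stay as they are.

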
 To demonstrate the effect of triptorelin embonate 22.5 mg 6-month formulation administered subcutaneously to suppress the 'acute-on-chronic' effect following the administration of the second dose 	
 Percentage of participants castrated on Day 3 and Day 7 after each injection administered on Day 1 and Day 169 (castration defined as testosterone <1.735 nmol/L (50 ng/dL))

 To demonstrate the effect of triptorelin embonate 22.5 mg 6-month formulation administered subcutaneously in the maintenance of PSA 	
 Percent change in PSA from baseline (prior to injection) at Day 169 and Day 337 (Percent change in PSA defined as the absolute value of difference between the PSA values at Day 169 and Day 337 and the baseline value divided by the baseline value)

Associated Procedure / Instruction Reference	319480-SOP
Form Reference	080091-FOR v7.0

Objectives	Endpoints

 To demonstrate the safety profile of triptorelin embonate 22.5mg 6-month formulation administered subcutaneously 	
 Incidence of TEAEs (including local tolerability) throughout the study i.e. up to Day 337 Change from baseline in clinical safety laboratory parameters (blood chemistry and haematology) at Day 337 Change from baseline in physical examination at Day 169 and Day 337 Change from baseline in ECG at Day 337 Change from baseline in vital signs (blood pressure and heart rate) at each visit up to Day 337

AE=adverse event; ECG=electrocardiogram; PSA=prostate-specific antigen; TEAE=treatment-emergent adverse event

Note: A list of laboratory parameters to be assessed during the study are presented in Protocol Appendix 10.2.

- Hypotheses**

Hypotheses for this study are defined below.

The primary objective of this study is to evaluate the efficacy triptorelin embonate 22.5 mg (6-month formulation) administered subcutaneously in maintaining serum testosterone castrate levels during the study (maintenance of castration defined as testosterone <1.735 nmol/L (50 ng/dL) at Day 29, Day 85, Day 141, Day 169, Day 253, Day 309 and Day 337) with two complete study intervention administrations. Thus, the null hypothesis to be tested is as follows:

Null hypothesis: percentage of participants castrated (serum level of testosterone <1.735 nmol/L) from date of first dose to Day 337 is less than or equal to 90%.

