2.3 Sample Size Determination and Power

This single-arm study is designed to demonstrate that the percentage of participants remaining castrated (maintenance of castration defined as testosterone <1.735 nmol/L (50 ng/dL) at Day 29, Day 85, Day 141, Day 169, Day 253, Day 309 and Day 337) during the study is greater than 90%. Considering an observed castration maintenance in 97% of participants, 130 eligible participants are required to demonstrate the efficacy of the triptorelin 6-month formulation with approximately 90% power and a one-sided alpha of 0.025 using an exact binomial test. The objective will be achieved if the lower bound of the 95% confidence interval (CI) of the observed rate is greater than 90%.

Considering a drop-out rate of 10%, 145 participants will be included in the study.

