4 ANALYSIS SETS

Screened Set

The screened set will contain all participants who signed an informed consent for this study. In case of re-screening, the participant will be counted once only in the screened set. The previous site and assigned subject numbers will be collected to link the first and second screening data.

Enrolled Set

The enrolled set will contain all participants who were enrolled to study treatment. A participant will be considered as enrolled if he has signed the informed consent form and is assigned to treatment.

Intent-to-Treat Set

The intent-to-treat (ITT) Set will contain all participants who signed an informed consent form and received at least one administration of study intervention and have a serum testosterone level <1.735 nmol/L (50 ng/dL) on Day 1 (pre-dose measurement).

Full Analysis Set

The full analysis set (FAS) will contain all participants who signed an informed consent form and received two administrations of study intervention and completed all visits for testosterone measurement (Day 29, Day 85, Day 141, Day 169, Day 253, Day 309 and Day 337). Note, a participant will be included in the FAS if his testosterone measurement is ≥ 50 ng/dl before the end of treatment, end of study or withdrawn from study, whichever is earlier.

Per Protocol Set

The per protocol (PP) set will contain all participants from the FAS who did not experience any major protocol deviations that may interfere with efficacy evaluation (refer to section 5.3 for details regarding the management of deviations).

Safety Set

The safety set will contain all participants who receive at least one dose of study intervention.

Associated Procedure / Instruction Reference	319480-SOP
Form Reference	080091-FOR v7.0

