5.7 Efficacy

5.7.1 General Considerations

The FAS set will be used for efficacy analyses unless explicitly stated differently.

A listing of all efficacy data (raw and derived) will be provided (see listing detail conventions in [Appendix 4](#)).

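### By-timepoint and Day 3/7 castration rates are analysed in the FAS, so valid early samples are discarded because of later missed visits or withdrawal

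*SAP*

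**What the plan says.** SAP 5.7.1 sets the default: "The FAS set will be used for efficacy analyses unless explicitly stated differently". SAP 5.7.3.2 applies it to the secondary endpoints: "The same strategies as those for the primary estimand will be used for the main secondary analysis in the FAS".

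Under SAP 4 (and Protocol 9.3) a FAS member must have "received two administrations of study intervention and completed all visits for testosterone measurement", at Days 29, 85, 141, 169, 253, 309 and 337. The one exception is a man with a value of 50 ng/dL or more, who is kept even if incomplete. Intercurrent events 1 to 3 in SAP 5.7.2.1 match this. The testosterone values of men who leave the study, miss a planned sample or do not receive the second injection are set aside, unless there is evidence of a value of 50 ng/dL or more.

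The secondary endpoints in SAP 5.7.3.1 include castration at each of the seven visits, testosterone below 20 ng/dL at each of them, and "Percentage of participants castrated on Day 3 and Day 7 after each injection administered on Day 1 and Day 169". SAP 5.7.3.2 does not name the Day 3/7 endpoint in its list of binary endpoints, but no other set is given, so the FAS default applies.

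Sensitivity analyses S1 to S3 (SAP 5.7.2.3) concern the primary endpoint. The only secondary sensitivity analysis (SAP 5.7.3.4) is a Kaplan-Meier estimate for below 20 ng/dL during the study. No ITT or observed-data version of the by-timepoint or Day 3/7 rates is planned.

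**The concern.** Whether a Day 3, Day 7 or Day 29 result counts depends on events up to eleven months later, and on outcome. An incomplete man castrate throughout is removed. An incomplete man with one value of 50 ng/dL or more stays. A composite endpoint over seven visits gives some reason to look at completers, but a rate at one visit does not need the other six.

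The flare endpoint is the clearest case. Day 3 and Day 7 after the first injection describe an immediate response, yet they are reported only in men selected on attendance to Day 337 or on failure. At stake are a small distortion of these rates, wider intervals than the collected data allow, and valid results that appear only in listings.

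**Working it through.** **Plan's own figure.** SAP 2.3 gives "Considering an observed castration maintenance in 97% of participants, 130 eligible participants are required", with "approximately 90% power and a one-sided alpha of 0.025 using an exact binomial test". With a null rate of 90% (SAP 2.1) and n = 130, success needs at least 124/130 (95.4%, Clopper-Pearson lower bound 90.2%). Exact one-sided alpha is 0.0207 and power 0.903. At 123/130, alpha would be 0.0456 and the lower bound 89.2%. Drop-out: 130/0.9 = 144.4, rounded up to 145, as in "Considering a drop-out rate of 10%, 145 participants will be included in the study". The sample size reproduces and is not in question.

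**Below 50 ng/dL, early visit.** Let N men be sampled, f of them not castrate at that visit, and L later lost from the FAS. The lost men have no value of 50 ng/dL or more, so all L are castrate at the visit and all f are kept.

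- All observed: (N − f)/N
- FAS: (N − L − f)/(N − L)

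The documents give no by-visit rates, so f is assumed. N = 145 and L = 15 follow the plan's 10% drop-out. Intervals are 95% Clopper-Pearson.

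| f | FAS | All observed | Shift (points) |
|---|---|---|---|
| 1 | 129/130 = 99.2% (95.8–100.0) | 144/145 = 99.3% (96.2–100.0) | −0.08 |
| 3 | 127/130 = 97.7% (93.4–99.5) | 142/145 = 97.9% (94.1–99.6) | −0.24 |
| 5 | 125/130 = 96.2% (91.3–98.7) | 140/145 = 96.6% (92.1–98.9) | −0.40 |
| 10 | 120/130 = 92.3% (86.3–96.2) | 135/145 = 93.1% (87.7–96.6) | −0.80 |

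The design's 97% implies about 0.03 × 130 = 3.9 failures over all seven visits, so f of 1 to 3 at one visit fits the design. There the interval widens by 0.4 to 0.6 points.

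**Less favourable scenarios (assumed).** With f = 7, all observed is 138/145 = 95.2%, width 7.7 points. If 10%, 15% or 20% of the other 138 are lost (14, 21 or 28 men), the FAS gives 124/131 = 94.7%, 117/124 = 94.4% or 110/117 = 94.0%, with widths 8.5, 9.0 and 9.5. With f = 10, 135/145 = 93.1% becomes 122/132 = 92.4% (13 lost) down to 108/118 = 91.5% (27 lost). The shifts run from about 0.5 to 1.6 points.

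**Below 20 ng/dL.** FAS entry stays tied to 50 ng/dL. SAP 5.7.3.2 replaces the castration criterion where applicable but does not redefine the FAS. An incomplete man at 20 to below 50 ng/dL is therefore removed although he fails this endpoint. Assume 15 removed and 10 of the 130 FAS men at 20 or above, so the FAS rate is 120/130 = 92.3%. If g of the removed men are also at 20 or above, all observed is (135 − g)/145:

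- g = 0: 93.1%
- g = 1: 92.4%
- g = 3: 91.0%
- g = 5: 89.7%

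The FAS is too low for g = 0 or 1 and too high for g = 3 or 5.

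**How the loss varies by visit.** A drop-out loses measured results only at visits before he left. If 15 drop-outs leave evenly between Day 1 and Day 337 (assumed), those measured at day d and lost afterwards number 15 × (337 − d)/336: 13.75 at Day 29, 7.5 at Day 169 and 1.25 at Day 309. Isolated missed samples do not shrink in this way, because they remove the man's results at every other visit. At an assumed independent 2% per visit, 1 − 0.98^7 = 13.2% of men miss at least one of seven.

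**Late visits.** Assume 4 of 130 men fail and are withdrawn under Protocol 7.2 before Day 253. A Day 337 rate among sampled men only would be 126/126 = 100%. Keeping the four as non-castrate gives 126/130 = 96.9%.

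**The case against.** The strongest objection concerns late visits. Protocol 7.2 withdraws men with confirmed inadequate suppression, so they have no later sample. The FAS keeps them, and SAP 5.1.2 by default counts participants with missing data in percentages. A denominator of sampled men only would drop them, and the 3.1-point upward error above exceeds every shift computed for the FAS below 50 ng/dL. This stands, and the fix allows for it.

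The size is also small. Seven men at 50 ng/dL or more at one Day 29 to Day 337 visit, with 14 others lost, caps the primary result at 124/131, lower bound 89.3%, so the trial would already have missed its criterion. Day 3/7 values lie outside the primary endpoint, so that limit does not reach them. At rates consistent with the design the shift is 0.1 to 0.2 points. This stands too.

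The analysis is descriptive, no success rule attaches to these endpoints, all efficacy data are listed, and below 50 ng/dL the early bias works against the product. That lowers the priority. It gives no reason to leave valid results out of the tables, and the conservative argument does not carry over to 20 ng/dL.

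The wide analysis windows in SAP 6.1 reduce missed visits but do nothing for drop-outs.

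**Conclusion.** The point holds in a limited form. Early-visit and Day 3/7 rates are selected on later attendance and on outcome, and no planned analysis shows them otherwise. Below 50 ng/dL the early-visit bias is downward, about 0.1 to 0.2 points at design-consistent rates and 0.5 to 1.6 points in the less favourable scenarios. Below 20 ng/dL the sign is open.

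A reader might infer three stronger things that the documents do not support:

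- That all these rates are biased downward. This fails at 20 ng/dL, because FAS entry is tied to 50.
- That 10% or more of measured men are lost at every visit. The 10% is planned drop-out. The loss it causes approaches that figure only at the earliest visits and shrinks later.
- That the FAS serves no purpose here. At late visits it keeps withdrawn failures in view.

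The sizes rest on assumed by-visit rates and losses. They also assume that any value of 50 ng/dL or more, including at Day 3 or 7, keeps a man in the FAS, as its note reads. Whether a missed Day 3, 7, 171 or 175 sample counts as a missed planned measurement under intercurrent event 2 is unclear and should be stated.

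**What to change.** In SAP 5.7.3.2, replace the FAS for these endpoints as follows:

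- **Day 3/7 after the first injection, and by-timepoint visits to Day 169 (below 50 and below 20 ng/dL):** all treated participants, or the existing ITT set, with a sample in that visit's analysis window. Name one of the two; the ITT set also requires a castrate pre-dose value on Day 1.
- **Day 171/175:** all who received the second injection and have a sample.
- **Day 253 to Day 337:** the same treated or ITT population, with men withdrawn for inadequate testosterone suppression under Protocol 7.2 kept in the denominator as non-castrate. Protocol 7.2 can also lead to withdrawal before Day 169, so apply the same rule to any by-timepoint visit after such a withdrawal.

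Report the denominator and missing count at each visit, and keep the FAS version as supportive. Name the Day 3/7 endpoint explicitly in 5.7.3.2.

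The cost is a change of population in a few tables and a SAP amendment before database lock. It needs no new data, and the primary analysis and sample size are unaffected. Protocol 9.4.2 names no analysis set for the secondary endpoints, so its text need not change.

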2.2 Background

Prostate cancer is the second most common cancer in the male population and thus the sixth cause of death from cancer in men over 50 in the western world [Sung 2021]. Prostate cancer is androgen dependent, with most patients initially responding to androgen deprivation therapy (ADT). However, after 1 to 2 years of treatment, advanced prostate cancer eventually progresses to castration resistant prostate cancer.

Androgen receptor signalling plays an important role in the development of prostate cancer. Gonadotropin-releasing hormone, also known as luteinizing hormone releasing hormone (LHRH) is released in a pulsatile manner by the hypothalamus and stimulates the pituitary to release in pulses the gonadotropins luteinizing hormone (LH) and follicle stimulating hormone (FSH). LH stimulates the production of testosterone by the testis; however, approximately 5% of circulating testosterone is independently produced by the adrenal glands. FSH plays a role in the regulation of spermatogenesis.

Since the pioneering studies of Huggins and Hodges [1941, 1941a] in the 1940's about the role played by the testicular androgen development and progression of prostate cancer cells, the mainstay of treatment for advanced prostate cancer has been androgen deprivation by bilateral orchiectomy and/or oestrogen therapy. The limitations of these therapeutic modalities led to the development of GnRH analogues, which have made pharmacological castration the preferred option among many patients with metastatic disease [Filicori 1994].

The therapeutic activity of the GnRH agonists is achieved via pituitary down-regulation of their own receptors achieved by continuous and chronic administration, providing almost complete suppression of LH and FSH secretion leading to suppression of testicular function.

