5.7.3.4 Sensitivity Analysis

For castration maintenance (<20 ng/dL) rate during the study, the Kaplan-Meier estimate at Day 337 using the same strategies as Primary-S3 with castration maintenance criteria replacing with as <20 ng/dL will be provided.

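### Percent change in PSA is summarised in a set defined by testosterone completeness, so valid PSA values are discarded and PSA maintenance can be overstated, mainly at Day 169

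*SAP*

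**What the plan says.** Percent change in PSA at Day 169 and Day 337 is a secondary efficacy endpoint (SAP 5.7.3.1). The general rule in SAP 5.7.1 is "The FAS set will be used for efficacy analyses unless explicitly stated differently", and SAP 5.7.3.2 repeats it for the secondary endpoints: "The same strategies as those for the primary estimand will be used for the main secondary analysis in the FAS". The only PSA-specific instruction is "For percent change in PSA from baseline at Day 169 and Day 337, descriptive statistics will be provided".

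Under SAP 4, FAS members must have "received two administrations of study intervention and completed all visits for testosterone measurement" at seven named days. The Note adds one exception: "a participant will be included in the FAS if his testosterone measurement is" 50 ng/dL or higher.

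The estimand in SAP 5.7.2.1 matches this. ICE 1 is "Subjects discontinued from study prior to Day 337 without evidence of inadequate testosterone suppression". ICE 2 is a missing planned testosterone value and ICE 3 is stopping before the second injection, both again without a testosterone failure. All three groups are left out of the main analysis.

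The ITT set is used only for the three sensitivity analyses of the primary endpoint (SAP 5.7.2.3). The single secondary sensitivity analysis concerns a testosterone threshold: "For castration maintenance (<20 ng/dL) rate during the study, the Kaplan-Meier estimate at Day 337" (SAP 5.7.3.4). None is planned for PSA.

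The Schedule of Activities (Protocol 1.3) has PSA drawn on Day 1, on Day 169 and at the end-of-study or early-discontinuation visit.

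**The concern.** The set was built for a testosterone endpoint and is carried over to PSA, where its conditions have no bearing on whether a PSA value is valid. A Day 169 value drawn on schedule is kept or discarded according to what the man does over the following 24 weeks.

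The loss may also be selective. The exception for testosterone failures retains men who escape castration. It does not retain a man who stays castrate while his disease progresses and who then leaves. Protocol 2.2 notes as background that "after 1 to 2 years of treatment, advanced prostate cancer eventually progresses to castration resistant prostate cancer", so such men can exist. They would be men whose PSA was not maintained, in a table meant to support an objective about maintenance of PSA.

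**Working it through.** **1. The plan's own figure.** No figure is stated for PSA. The sample-size statement (SAP 2.3) supplies the number of men at issue, and it reproduces:
- With n = 130, a null rate of 90% and one-sided alpha 0.025, success needs at least 124 of 130. The exact lower 95% limit is 0.902 at 124 and 0.892 at 123.
- The exact alpha is 0.0207, and power at 97% is 0.903.
- 130 / 0.90 = 144.4, rounded up to 145. The planned loss is 145 − 130 = 15 men.

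**2. Who loses PSA data, reading the rules as written** (testosterone below 50 ng/dL throughout):

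| Man | PSA collected | In FAS? |
|---|---|---|
| Misses the Day 85 testosterone sample, attends everything else | Day 1, 169, 337 | No (ICE 2) |
| Leaves after Day 169 | Day 1, 169, early-discontinuation sample | No (ICE 1) |
| Has Day 169 PSA, no second injection | Day 1, 169 | No (ICE 3) |

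The excluded PSA values would appear only in listings.

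**3. Which timepoint is affected.** SAP 5.1.1.1 applies the analysis windows to PSA, and in SAP 6.1 the Day 337 window opens 155 days after the second injection. An early-discontinuation sample drawn before that does not count as Day 337. Early leavers therefore have no Day 337 value in any analysis set. The recoverable selective loss is mainly at Day 169, among men who reach that visit and leave later.

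**4. Illustrative size.** These inputs are assumptions, not document figures: log PSA ratio Normal(0, 0.5²) in other men, and k men who leave with PSA exactly doubled (+100%). All 145 are given a value at the timepoint.
- Signed change (SAP 7, item 7). The FAS mean is exp(0.5²/2) − 1 = 13.3%. The all-men mean is [(145 − k) × 13.3 + k × 100] / 145. For k = 5: (140 × 13.3 + 500) / 145 = 16.3%.
- Absolute change (SAP 5.7.3.1). With Φ the standard normal distribution function, the FAS mean is exp(0.125) × [Φ(0.5) − Φ(−0.5)] = 1.133 × 0.383 = 43.4%. For k = 5: (140 × 43.4 + 500) / 145 = 45.3%.
- Medians and quartiles are quantiles of the same mixture.

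| k | Signed mean | Signed upper quartile | Absolute mean | Absolute median |
|---|---|---|---|---|
| 0 (equals FAS) | 13.3% | 40% | 43.4% | 32.7% |
| 1 | 13.9% | 41% | 43.8% | 32.9% |
| 3 | 15.1% | 44% | 44.6% | 33.5% |
| 5 | 16.3% | 46% | 45.3% | 34.0% |
| 10 | 19.3% | 54% | 47.3% | 35.4% |
| 15 | 22.3% | 63% | 49.2% | 37.0% |

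The direction is the same under both definitions, but the absolute-value definition mutes the effect. The rows for k = 10 and 15 are extremes: most or all of the planned losses would have to be men who reached Day 169 with PSA already doubled and then left.

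**The case against.** The strongest counter-argument is that selective loss is assumed, not shown. Protocol 7.2 allows withdrawal at the man's request, or at the investigator's discretion for safety, behaviour or compliance, and requires it for inadequate testosterone suppression. Rising PSA is not a listed reason, and the men withdrawn for testosterone are kept in the FAS by the Note. Protocol 6.8 permits several added treatments, so a man with rising PSA may stay. Protocol 5.1 and 5.2 exclude metastatic castration-resistant and high-burden disease and require a life expectancy above 18 months. The sentence in Protocol 2.2 is general background and gives no rate for this cohort. All of this stands. A reader might infer that PSA maintenance will be overstated, at both timepoints and by a material amount. The documents support only that it can be, and mainly at Day 169.

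It can also be said that the table is descriptive, with no threshold or test, and that efficacy data, withdrawal reasons and reasons for exclusion from each set are all reported. This is right and limits the consequence. It does not justify leaving valid values out of the only PSA summary, because a reader would have to rebuild the fuller summary from listings.

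Men with testosterone failure are retained and so slightly over-represented: 4 failures, for example, would be 4/130 = 3.1% rather than 4/145 = 2.8%. That may pull the other way, but it is small.

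**Conclusion.** The point holds in a limited form. It is certain from the text that valid, on-schedule PSA values are discarded for reasons unrelated to PSA, and that no planned analysis brings them back. That the summary can overstate PSA maintenance is conditional on some castrate men leaving with rising PSA. If loss is unrelated to PSA there is no bias, only fewer usable values.

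The size cannot be determined from the documents. Under the assumed distribution, 1 to 3 affected men move the signed mean by about 1 to 2 percentage points and the absolute median by less than 1 point. The extreme of 15 moves them by about 9 and 4 points. The testosterone endpoint and the primary conclusion are unaffected. The change is worth making because it is nearly free and lets a reader see whether the exclusion mattered.

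**What to change.** In SAP 5.7.3.2, state the following for PSA:
- Percent change at Day 169 and Day 337 is summarised in the Safety Set, in all men with a pre-dose PSA and a PSA value at the timepoint, without the ICE 1 to 3 exclusions. The number of men is shown at each timepoint.
- For men who leave before Day 337, the last observed PSA, including the early-discontinuation sample, is summarised separately. The first summary cannot give these men a Day 337 value.
- The FAS summary is kept as supportive.

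The Safety Set is suggested because it sets no testosterone condition. The ITT set requires a castrate Day 1 testosterone value.

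The cost is a short SAP amendment and one or two extra descriptive tables from data already collected. The small downside is that the PSA population then differs from that of the testosterone endpoints, which a table footnote can explain.
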